### **Screening**

All study participants must be thoroughly informed about all aspects of the study, including the study treatment, visit schedule, required evaluations, and all regulatory requirements for informed consent. Written informed consent must be obtained before any study specific assessments are performed, including screening. If the participant is unable to read, an impartial witness should be present during the entire informed consent discussion.

All screening assessments must be performed within 1 to 28 days prior to randomization or within 1 to 14 days prior to randomization for selected assessments (see [Table 8-2](#) for the list of assessments to be performed) to confirm patient's eligibility.

Any screening assessment that is done outside the screening window, as defined in [Table 8-2](#), must be repeated prior to randomization.

A new ICF will need to be signed if the Investigator chooses to re-screen the participant after a participant has screen failed. In case of re-screening, a new participant ID will be generated, however, site has to provide original participant ID in respective re-screening eCRF to link the two participants for reporting and validation.

All required screening activities must be performed when the participant is re-screened for participation in the study to satisfy the requirements defined in [Table 8-2](#). An individual participant may only be re-screened once for the study. Once the number of participants screened and enrolled/randomized is likely to ensure target enrollment, Novartis may close the study to further screening. In this case, the participants who screen failed will not be permitted to re-screen.

A participant who has a laboratory test result(s) that does not satisfy the entrance criteria may have the test(s) repeated. These test(s) may be repeated as soon as the Investigator believes the retest result(s) is/are likely to be within the acceptable range to satisfy the entrance criteria, but should be completed within 14 days of screening period, as defined in [Table 8-2](#). In this case, the participant will not be required to sign another ICF, and the original participant ID number assigned by the Investigator will be used. In the event that the laboratory test(s) cannot be performed within 14 days of screening period, as defined in [Table 8-2](#) or the re-test(s) do not meet the entrance criteria, or other eligibility criteria have changed and are not met anymore, the participant is considered a screen failure. Unused tumor samples for screen failure participants will be returned, unless otherwise directed. In case re-screening occurs, all evaluations re-assessed should meet the eligibility criteria.

Any imaging assessments already completed during the regular work-up of the participant and within 28 days prior to randomization (42 days prior to randomization for whole body scan), including before signing the main study ICF can be considered as the baseline images for this study.

### **8.1.1 Eligibility screening**

Following IRT registration at molecular pre-screening and screening, participants' eligibility will be checked according to study inclusion and exclusion criteria as described in [Section 5](#) once all screening procedures are completed.

A list of procedures to be performed during the 28-day screening period is summarized in [Table 8-2](#).

Results of all screening/baseline evaluations must be reviewed by the Investigator or his/her designee prior to start study treatment of each participant to ensure that all inclusion and exclusion criteria have been satisfied. When all screening procedures are completed and the participant's eligibility is confirmed (i.e. all inclusion/exclusion criteria have been verified), the key eligibility criteria checklist embedded in the IRT system will be completed prior to the first dose of study drug. Please refer to [Section 6.4.2](#) and as well as comply with detailed guidelines in the IRT user guide.

### **8.1.2 Information to be collected on screening failures**

[figure not shown]
Participants who signed an informed consent form and subsequently found to be ineligible prior to randomization will be considered a screen failure. This can be either after the signature of the molecular pre-screening ICF or after the signature of the main study ICF.

The screening phase discontinuation status should be recorded on the appropriate eCRF. Demographic information, informed consent, and Inclusion/Exclusion pages must also be completed for screen failure participants. No other data will be entered into the clinical database for participants who are screen failures, unless the participant experienced a serious adverse event during the screening phase (see [Section 10.1.3](#) for reporting details). If the participant fails to be randomized, the IRT must be notified within 2 days of the screen fail that the participant was not randomized.

Participants who are randomized and fail to start treatment, e.g., participants randomized in error, will be considered as early terminators. The reason for early termination should be recorded on the appropriate Case Report Form.

## **8.2 Participant demographics/other baseline characteristics**

Country-specific regulations should be considered for the collection of demographic and baseline characteristics in alignment with eCRF.

The following participant demographics and baseline characteristics are to be collected on all enrolled/randomized participants:

- Demographic information age, sex, race/predominant ethnicity (if permitted). Participant race/ethnicity data are collected and analyzed to identify any differences in the safety and/or efficacy profile of the treatment due to these characteristics. In addition, we need to assess the diversity of the study population as required by Health Authorities.
- Medical history (e.g., important medical, surgical, and allergic conditions from the participant's medical history which could have an impact on the participant's evaluation)/current medical conditions (e.g., all relevant current medical conditions which are present at the time of signing informed consent). Ongoing medical conditions, symptoms and disease which are recorded on the Medical History eCRF should include the toxicity grade. Where possible, the diagnosis and not symptoms should be recorded.
- Disease baseline characteristics including diagnosis, history, extent of cancer with ER, PgR and HER2 status, staging of cancer, all prior antineoplastic therapies including surgical interventions and chemo-, biologic-, immunologic- and radiation-therapies provided as treatment for cancer prior to the administration of study drug
- Prior/concomitant therapy: all prescription medications, over-the and significant non-drug therapies taken within 30 days before the first dose is administered. They must be recorded on the Prior and Concomitant medication or Prior or Concomitant non-drug therapies/procedures eCRF page and updated on a continual basis if there are any new changes to the medications. See the protocol [Section 6.2.1](#) Concomitant Therapy for further details on what information must be recorded on the appropriate page of the eCRF.

Furthermore, the following assessments will be performed to assess the eligibility of the participant:

- Body height, body weight and abdominal girth
- Vital signs including blood pressure (supine position preferred when ECG is collected), pulse measurement, and body temperature
- ECOG Performance Status
- 12-Lead ECG
- Cardiac imaging (MUGA or ECHO)
- Tumor evaluation (e.g., CT Scan)
- Whole body bone scan
- Laboratory evaluations (e.g., hematology, coagulation, biochemistry, fasting insulin level, fasting glucose/serum lipid profile/HbA1c/lipase/amylase, ketones, urinalysis)
- The presence of a PIK3CA mutation(s) in the tumor (tissue or plasma)
- Complete physical examination

## 8.3 Efficacy

### 8.3.1 Efficacy assessment 1

#### Efficacy assessments

Tumor response will be assessed locally according to the Novartis guideline version 3.2 ([Section 16.4](#)) based on RECIST 1.1 ([Eisenhauer et al 2009](#)). The imaging assessment collection plan is presented in [Table 8-3](#).

Imaging data for all participants will be assessed locally and the results of the local evaluations will be used to support the secondary objective.

The local Investigator's assessment will be used for treatment decision making.

If needed imaging data will be centrally collected and checked for quality by an imaging Contract Research Organization (CRO) designated by Novartis. Central review of the imaging data may be performed if deemed necessary.

Information regarding prior interventions (e.g., radiotherapy), pre-existing radiographic findings that mimic metastatic disease at baseline/screening and prior interventions should be transmitted to the imaging CRO via the Baseline Clinical Form along with the baseline images. Sites will ensure the data entered on the form is consistent with the data entered in the clinical database.

Physical exam tumor assessments, photography, pathology/histology and cytology results, as well as, information regarding prior interventions, pre-existing radiographic findings that mimic metastatic disease at baseline/screening and on-study interventions should be captured in the appropriate eCRFs.

All known lesions (measurable, non-measurable) should be accounted for at screening within 28 days (42 days for whole body bone scan) before Cycle 1 Day 1 when assessing objective tumor status. Imaging assessments for response evaluation will be performed every 8 weeks (+/- 7 days) after randomization. The 8-week interval should be respected regardless of whether study treatment is temporarily withheld or unscheduled assessments are performed. Assessment modality must remain the same throughout the study (e.g., contrast CT or MRI scan) using RECIST 1.1 criteria.

**Table 8-3 Imaging Assessment Collection Plan**

Procedure	Screening/Baseline	During Treatment/Follow-up
Chest, abdomen and pelvis CT or MRI (with intravenous contrast enhancement)	Mandated	Mandated, every 8 weeks (+/- 7 days) until disease progression, EOT  , death, withdrawal of consent/opposition to use data/biological samples, or lost to follow-up
Brain CT or MRI	Mandated at screening only if existing or suspected brain metastasis	If lesions were documented at baseline, follow same schedule as CT/MRI of chest, abdomen, and pelvis
Whole body bone scan	Mandated, within 42 days (6 weeks) prior to randomization	If clinically indicated

Procedure	Screening/Baseline	During Treatment/Follow-up
Localized bone CT, MRI, or x-ray	Mandated for skeletal abnormalities identified on the whole body bone scan that are not visible on the chest, abdomen and pelvis CT or MRI	If lesions were documented at baseline, follow same schedule as CT/MRI of chest, abdomen, and pelvis
Color photography (with scale/ruler)	Mandated if any skin lesions present at screening	If lesions were documented at baseline, follow same schedule as CT/MRI of chest, abdomen, and pelvis
CT or MRI of other metastatic sites (e.g., neck)	Mandated if suspected lesion at screening	If lesions were documented at baseline, follow same schedule as CT/MRI of chest, abdomen, and pelvis

 Tumor evaluation at End of treatment (EOT) is required for participants who discontinue study treatment before the first scheduled post-baseline tumor assessment (week 8) and for participants whose previous tumor assessment did not demonstrate progressive disease (PD) and was done more than 21 days prior to EOT visit

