Key Exclusion criteria	

Participant who relapsed with documented evidence of progression more than 12 months from completion of (neo)adjuvant endocrine therapy with no treatment for metastatic disease

Participant had more than 1 line of prior treatment in the metastatic setting

Participant has received prior treatment with chemotherapy (except for neoadjuvant/adjuvant chemotherapy), any PI3K, Mammalian Target of Rapamycin (mTOR) or Protein Kinase B (Akt) inhibitor

Participant has inflammatory breast cancer at screening

Participant with an established diagnosis of diabetes mellitus type I or participants with type II diabetes mellitus requiring antihyperglycemic therapy

Participant has a history of acute pancreatitis within 1 year of screening or a past medical history of chronic pancreatitis

Participant has currently documented pneumonitis/interstitial lung disease

Participant has a history of severe cutaneous reaction, such as Steven-Johnson Syndrome (SJS), erythema multiforme (EM), Toxic Epidermal Necrolysis (TEN) or Drug Reaction with Eosinophilia and Systemic Syndrome (DRESS)

Study treatment	

Arm A: Alpelisib (BYL719) + fulvestrant + dapagliflozin + metformin XR

Arm B: Alpelisib (BYL719) + fulvestrant + metformin XR

Efficacy assessments	

Chest, abdomen, and pelvis computerized tomography (CT) or magnetic resonance imaging (MRI) with intravenous contrast enhancement at screening and every 8 weeks (+/- 7 days) until disease progression, end of treatment (EOT), death, withdrawal of consent/opposition to use data/biological samples, or lost to follow-up

Key safety assessments	

Physical examination

Body weight, height, abdominal girth and vital signs

ECOG performance status

Laboratory evaluations, including hematology, biochemistry, coagulation, and urinalysis

Electrocardiogram (ECG)

Cardiac imaging (multigated acquisition scan (MUGA) or echocardiogram (ECHO))

Adverse events (AEs) with severity, relationship to study treatment and seriousness

Skin photographs and skin biopsies (strongly recommended for Grade 3 and mandatory for Grade 4 skin toxicities)

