### Figure 3-1 Study Design

**Figure 3-2** Study Flow Chart

The primary endpoint is the occurrence of severe (Grade  $\geq 3$ ) hyperglycemia events (based on glucose laboratory values) over the first eight weeks of alpelisib plus fulvestrant (from Cycle 1 Day 8 to Cycle 3 Day 8) with prophylactic treatment with dapagliflozin plus metformin XR compared to alpelisib plus fulvestrant with prophylactic metformin XR in participants who have at least one baseline risk factor associated with severe hyperglycemia.

The study will consist of 4 phases: molecular pre-screening, screening (28 days), randomized treatment, and post-treatment follow-up (safety follow-up and efficacy follow-up if applicable) as described in the study flow chart ([Figure 3-2](#)).

Treatment with fulvestrant and dapagliflozin plus metformin XR or metformin XR will be initiated on Cycle 1 Day 1 and be administered continuously. Alpelisib treatment begins one

week after the start of antihyperglycemic therapy (Cycle 1 Day 8) to allow for initial titration prior to alpelisib dosing.

The duration of treatment with alpelisib and fulvestrant will be 12 cycles or until disease progression, unacceptable toxicity, or discontinuation from study treatment for any other reason, whichever comes first. A cycle of treatment is defined as 28 days.

After treatment discontinuation, all participants will enter the safety follow-up which will end 30 days after participant discontinues from study treatment.

Participants who discontinue for reasons other than disease progression, death, lost to follow-up, or withdrawal of consent/opposition to use of data/biological samples before completing 12 cycles of treatment will additionally enter post-treatment efficacy follow-up. Post-treatment efficacy follow-up will end 12 cycles after randomization.

After the 12 cycles treatment period for alpelisib plus fulvestrant, participants who, in the opinion of the Investigator, are benefiting from study treatment may switch to commercially available supply.

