### **Post baseline imaging assessments**

Imaging assessments as described in [Table 8-3](#) should be performed using the same imaging modality used at baseline, irrespective of study treatment interruption or actual dosing (see [Table 8-2](#)). Imaging assessments for response evaluation will be performed every 8 weeks (+/- 7 days) until disease progression, death, lost to follow-up or withdrawal of consent/opposition to use data/biological samples. Imaging assessments should be scheduled using the randomization date as the reference date (not the date of the previous tumor assessment), and should be respected regardless of whether treatment with study treatment is temporarily withheld or unscheduled assessments performed.

All participants who discontinue from study treatment due to disease progression must have their progression clearly documented according to RECIST 1.1 as assessed by Investigator. If a participant did not discontinue study treatment due to disease progression per RECIST 1.1 assessed by Investigator, death, lost to follow-up, or withdrawal of consent/opposition to use data/biological samples, then tumor assessments should continue to be performed according to the planned schedule during efficacy follow-up for 12 cycles after randomization or until disease progression (per Investigator), death, lost to follow-up or withdrawn consent/opposition to use data/biological samples.

An additional tumor assessment must be performed to confirm response (complete response (CR) or partial response (PR)) no less than 4 weeks after the criteria for response are first met.

Additional imaging assessments may be performed at any time during the study at the Investigator's discretion to support the efficacy evaluations for a participant, as necessary. Clinical suspicion of disease progression at any time requires a physical examination and imaging assessments to be performed promptly rather than waiting for the next scheduled imaging assessment.

Each lesion that is measured at baseline must be measured by the same method (either same imaging method or by photography, including a metric ruler) and when possible, the same local radiologist/physician throughout the study so that the comparison is consistent. If an off-schedule imaging assessment is performed because progression is suspected, subsequent imaging assessments should be performed in accordance with the original imaging schedule.

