3.1 Primary endpoint(s)

The sample size calculation is based on the primary endpoint occurrence of severe hyperglycemia. The hypotheses to be tested and details of the testing strategy are described in [Section 2.5.2](#).

The incidence of severe hyperglycemia adverse events over the first eight weeks of alpelisib plus fulvestrant treatment in the study treatment arm B (i.e. prophylactic metformin XR alone) is assumed to be 40% based on data from the SOLAR-1 study in HR-positive, HER2-negative, advanced breast cancer participants with a PIK3CA mutation treated with alpelisib plus fulvestrant.

It is expected that treatment with prophylactic dapagliflozin plus metformin XR will result in a 20% reduction in the incidence rate. Approximately 124 participants (62 in each arm) will be required to detect a 20% difference in incidence rate with 80% power using the difference of proportion test at a one-sided 5% level of significance ([Table 3-1](#)). Assuming a 5% dropout rate (participants without adequate assessment of glucose laboratory values per protocol from Cycle 1 Day 8 to Cycle 3 Day 8) at the time of primary analysis, approximately 132 participants will need to be randomized to the two treatment arms in a 1:1 fashion.

Table 3-1 Sensitivity of power to changes in assumptions for N=124

Expected reduction in incidence rate	Observed reduction in incidence rate	Power
20%	30%	99.2%
	25%	93.8%
	20%	79.1%
	15%	56.1%
	10%	32.0%
	5%	14.2%

Note: Simulations are performed in East 6.4 with number of simulations = 100,000 and randomization seed = 2020.

4 Change to protocol specified analyses

Due to the permanent halt of recruitment and early termination of study, the primary analysis will not be conducted. Instead,

- the primary endpoint will only be summarized descriptively without any supplementary analysis.
- the secondary efficacy endpoint, PFS will only be listed without summaries.
- the secondary efficacy endpoints ORR and CBR will only be listed without summaries.
- there will be no subgroup analyses for efficacy and safety endpoints
- the study treatment such as exposure and dose intensity will only be listed without summaries.
- for safety endpoints, only adverse events, deaths and serious adverse events will be summarized. Other safety endpoints will only be listed for participants with notable values.

5 Appendix

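### Table 8-3 and the protocol summary end 8-weekly tumour imaging at end of treatment, while Sections 8.3.1 and 9.1.1 and Table 8-2 continue it after early discontinuation

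*Protocol*

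**What the plan says.** Two places make EOT a stop for imaging:

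- Protocol Table 8-3, chest/abdomen/pelvis row, in a column that covers both treatment and follow-up: "Mandated, every 8 weeks (+/- 7 days) until disease progression, EOT", followed by death, withdrawal and loss to follow-up. The brain, localized bone, skin photography and other-site rows refer back to this schedule.
- Protocol summary, efficacy assessments: "every 8 weeks (+/- 7 days) until disease progression, end of treatment (EOT), death", followed by withdrawal and loss to follow-up.

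Three places carry imaging past EOT:

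- Section 8.3.1, post-baseline imaging. Its general stop list omits EOT. For participants who stopped treatment for a reason other than progression, death, loss to follow-up or withdrawal, it adds that "tumor assessments should continue to be performed according to the planned schedule during efficacy follow-up for 12 cycles after randomization", unless one of those events comes first.
- Section 9.1.1 repeats that rule where treatment discontinuation is described.
- Table 8-2 has 8-weekly tumour assessment in its efficacy follow-up column. It names neither EOT nor a 12-cycle limit as a stop.

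Section 3 sets the period. Participants who stop for such other reasons "before completing 12 cycles of treatment will additionally enter post-treatment efficacy follow-up", and "Post-treatment efficacy follow-up will end 12 cycles after randomization". It does not mention scans itself.

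On analysis, protocol Section 12.5.1 measures PFS from randomization in the FAS, censors at the last adequate tumour assessment and plans PFS rates at 24 and 48 weeks. After recruitment was halted, SAP Section 4 states that "the secondary efficacy endpoint, PFS will only be listed without summaries".

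**The concern.** Section 8.3.1 names Table 8-3 as the imaging collection plan, so a site may reasonably work from it. A site that follows the table stops scanning at EOT. A site that follows the surrounding text continues. The same participant could therefore be followed for progression or not, depending on the page read.

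The participants caught by this are those who stop all anticancer study treatment early without progression, for example for toxicity. Where scanning stops with treatment, their PFS is censored at about the time they stopped. That censoring is linked to tolerability, which is a secondary objective and which the antihyperglycemic regimens are meant to improve (Section 4.5.1). If those who stop differ in progression risk from those who continue, the censoring is informative, and it could differ between arms.

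**Working it through.** The plan has no figure to reproduce here. The check is a comparison of texts plus the scan calendar.

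**1. Who reaches EOT.** Sections 6.1.5 and 9.1.1 equate EOT with stopping both alpelisib and fulvestrant. Section 6.1.4 lets a participant continue one drug and keep to the scheduled assessments. Section 8.3.1 says the same for those who stop alpelisib and stay on fulvestrant. The conflict therefore concerns only participants who stop both.

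**2. The rules side by side**, for a participant who stops both drugs early without progression:

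| Place | Scans after EOT? | Stated limit |
|---|---|---|
| Protocol summary | No | EOT |
| Table 8-3 | No | EOT |
| Table 8-2, efficacy follow-up column | Yes, 8-weekly | No time limit |
| Section 8.3.1 text | Yes, planned schedule | 12 cycles after randomization |
| Section 9.1.1 | Yes, planned schedule | 12 cycles after randomization |

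Table 8-3 sits inside Section 8.3.1, so that section contradicts itself. Footnote 1 of Table 8-3 says only when a scan at EOT is required: if treatment stops before the week-8 assessment, or if the previous scan showed no progression and was more than 21 days before the EOT visit. It is silent on what follows EOT.

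**3. Scans at stake.**
- 12 cycles x 28 days = 336 days, and 336 / 7 = 48 weeks.
- Scheduled post-baseline scans: 48 / 8 = 6 (weeks 8, 16, 24, 32, 40, 48).
- After the week-8 scan: 6 - 1 = 5.
- SAP Table 5-2 ends at Cycle 11 Day 1, week 40. On that calendar: 40 / 8 = 5 scans, and 5 - 1 = 4 after week 8.
- The loss for someone who stops soon after week 8 is therefore 4 to 5 scans.

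**4. PFS time, worked example.** Assume both drugs stop at week 10 without progression, with a week-8 scan done.
- The EOT visit is due within 14 days (Table 8-1), so the week-8 scan is then 14 to 28 days old. An EOT scan is required only if it is more than 21 days old.
- Under Table 8-3, PFS is censored at week 8, or by week 12 (10 + 2) if an EOT scan is done and shows no progression. Both are before the 24-week landmark.
- Under Sections 8.3.1 and 9.1.1, scans continue from week 16 to week 40 or 48. The participant can inform the 24-week rate and, if followed to the end, the later part of the curve.

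**5. Best response in the same example.** SAP Sections 2.6.1 and 5.4.2 use only scans within 30 days after the last dose. If week 10 is the last dose of any component (SAP Section 2.1.1.5), the window closes at about 10 + 30 / 7 = 14.3 weeks. The week-16 scan is already outside it, so the missed scans do not alter best response.

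**The case against.** The intended design can be recovered. The continuation rule is written out twice and scheduled once. Section 8 makes Table 8-2 the list of all assessments, and the Table 8-3 column heading includes follow-up. EOT in that table might be read as an extra scan time rather than a stop. This has some force, but the literal wording makes EOT an end of the schedule, the footnote does not rescue it, and the summary repeats EOT without any footnote. The same evidence does rule out the inference that efficacy follow-up contains no tumour assessment at all, because Table 8-2 places one there.

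A reader might also size the problem from Table 1-1. Discontinuation for hyperglycemia was 6% in SOLAR-1 and 2% in BYLieve Cohort A, so 132 x 0.02 = 2.6 to 132 x 0.06 = 7.9, or about 3 to 8 participants. The documents do not support that count. Section 4.3 describes the SOLAR-1 figure as 18 of 284 patients discontinuing alpelisib, and such participants may stay on fulvestrant and on the scan schedule. No rate for stopping both drugs is given for any cause, and recruitment ended early.

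It is also correct that EOT is not wrong for everyone. Section 3 sends only those who stop before completing 12 cycles into efficacy follow-up, so simply deleting EOT would leave completers with no stated end of imaging in Table 8-3.

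Finally, little analysis remains to be affected. Secondary endpoints were never to be tested, and the SAP drops the PFS analysis. A reader might infer a biased comparison of PFS between arms, but no such comparison will be made.

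**Conclusion.** The point holds as an internal inconsistency of minor weight. The protocol summary and Table 8-3 disagree with Section 8.3.1, Section 9.1.1 and Table 8-2 on whether imaging continues after early EOT. Section 3 supports continuation by defining the follow-up period. Appendix 16.4.3.2.1 points the same way: it treats follow-up for progression after stopping as usual and asks for any exception to be stated clearly in the protocol.

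For an affected participant the size is 4 to 5 missed scans and a PFS time censored near treatment stop. This assumes that both drugs stop soon after week 8 without progression and that the site follows Table 8-3. The number of such participants is unknown. What is affected now is which scans were done and how the listed PFS times should be read.

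**What to change.** In Table 8-3 and the protocol summary, replace EOT as a general stop with the Section 8.3.1 and 9.1.1 rule: participants who stop before completing 12 cycles for a reason other than progression, death, loss to follow-up or withdrawal continue 8-weekly imaging until 12 cycles after randomization, or until one of those events. Keep EOT as the end of imaging only for those who complete 12 cycles. Keep footnote 1. Add the same 12-cycle limit to the tumour assessment entry in the efficacy follow-up column of Table 8-2, and state whether a week-48 scan is due, since SAP Table 5-2 stops at week 40.

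The cost is a few wording edits, with no procedure beyond what Section 8.3.1 already requires. If the protocol will not be amended again, one sentence in the study report saying which rule sites applied would let the listed PFS times be interpreted. It would not recover scans already missed.
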